#### **6.5.2. Day 1 (Prior to surgery)**

The subjects will be admitted to the study unit on the morning of the surgical procedure and the following assessments will be conducted on the day of Check-in (Day 1 prior to surgery) for all subjects:

- Medical/Medicinal history update (Section 6.3.2)
- 12-lead ECG (Section 6.4.3)
- Measurement of resting vital signs (Section 6.4.2)
- Drug and alcohol screen (Section 6.4.1)
- Urine pregnancy test (Section 6.4.1)
- Eligibility assessment. Subjects who continue to meet pre-operative eligibility criteria will undergo two mandibular third molar extractions per Section 5.1.
- Patient training program for pain assessments (Section 6.3.5)
- Assessment and monitoring of AEs (Section 7)

#### **6.5.3. Day 1 (After surgery/Pre-dose Baseline)**

The following assessments will be conducted on Day 1 after surgery prior to administration of Dose 1 (T0) for all subjects while confined at the study clinic:

- Assessment of baseline pain intensity (4-point categorical pain intensity (PI) scale and 11-point numerical pain rating scale (NPRS) (Section 6.3.5)
- 12-lead ECG (Section 6.4.3)
- Measurement of resting vital signs pre-dose (Section 6.4.2)
- Pre-dose PK sample collection (Section 6.2)
- Randomization, if subject meets I/E criteria

- Monitoring of AEs and concomitant medication (Section 7)

Dosing: Subject who meet post-operative inclusion criteria and are randomized into the study will receive the study drug per randomization assignment within 15 minutes of meeting qualifying baseline pain scores. The time of the study drug administration will be designated as T0.

#### 6.5.4. Day 1 (Post Dose)

The following assessments will be conducted after surgery following administration of the study drug for all subjects while confined at the study clinic:

- 11-point Pain Intensity Numerical Rating Scale (NPRS) and 5-point Categorical Pain Relief Scale (PR) assessments at baseline, 15, 30, 45 minutes, and at 1, 1.5, 2, 3, 4, 5, 6, 7, and 8 hours after study drug administration (T0). (Sections 6.3.5 and 6.3.6)
- Measurement of time to pain relief via the ‘two stopwatch’ method (Section 6.3.7)
- Administer Patient Rating of Treatment satisfactoriness at 8 hours after study drug administration, prior to first rescue medication administration, and/or prior to early discontinuation. (Section 6.3.8)
- 12-Lead ECG at 1, 2, 4, and 8 hours after treatment initiation (Section 6.4.3)
- Measurement of resting vital signs at the following time points: at 1, 2, 4, and 8 hours after treatment initiation. (Section 6.4.2)
- A maximum of twelve 4\_mL blood samples will be taken from each participant at pre-dose and at 15, 30, and 45 minutes, and at 1, 1.5, 2, 2.5, 3, 4, 6, and 8 hours following dosing (Section 6.2).
- Clinical laboratory tests at 8 hours (Section 6.4.1)
- Physical examination at 8 hours (Section 6.3.3)
- Monitoring of AEs and concomitant medication (Section 7)

Pain assessments (NPRS, PR and Patient Assessment of Treatment satisfactoriness), clinical safety lab tests, and 12-lead ECG and other procedures that are scheduled at the 8-hour post dose time point should be collected at the time of early study termination (if it should occur).

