Subjects will be domiciled at the research facility during the first 8 hours after initiation of study drug treatment. For safety and welfare of the subject, the site may choose to have subjects stay overnight at the study center. An 11-point numerical pain rating scale (NPRS) will be used to determine the intensity of pain, 0-10 where 0 is ‘no pain’ and 10 is ‘worst imaginable pain’. NPRS

assessments will be performed at: baseline, 15, 30, and 45 minutes, and at 1, 1.5, 2, 3, 4, 5, 6, 7, and 8 hours after study drug administration (T0). Also at these time points, Pain Relief (PR) will be assessed using a 5- point categorical scale. (where 0= no pain relief, 1= little pain relief, 2= some pain relief, 3= a lot of pain relief, 4= complete pain relief). Numerical pain rating scale (NPRS) and pain relief (PR) assessments will also be completed before taking any dose of rescue medication, and at time of early discontinuation (if it occurs). The time to first perceptible pain relief and time to meaningful pain relief will be determined using the ‘two stop watch’ method. Subjects will also complete a Patient Rating of Treatment satisfactoriness at 8 hours after treatment initiation (prior to discharge from the clinical research center), or immediately prior to the time of first rescue analgesic administration, or at time of early discontinuation. Serial vital signs and 12 lead ECG will be done as indicated in Section 6.4.

For time points where several procedures are scheduled, the following sequence will be followed: 12-lead ECG, Vital signs, Pain assessments (where applicable), PK blood draw, clinical laboratory (where applicable).

Subjects with inadequately controlled pain symptoms may request 1-2 oxycodone 5 mg/acetaminophen 325 mg q 4 h as needed as rescue analgesic medication. For subjects who require additional analgesia, additional analgesic medication may be administered per the surgeon’s standard of care.

Post rescue analgesic administration, subjects will continue completing pain assessments until 8 hours after treatment initiation. However, these assessments will be disregarded in the statistical analysis.

Subjects should be encouraged to wait at least 2 hours after the first study drug administration before utilizing rescue analgesia, if possible. As much as possible, rescue analgesic medication should be administered only if pain intensity (PI) prior to rescue is  $\geq 4$  on the numerical rating scale.

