##### **8.3.2.1. PI and PR Scores Before and After Analgesic Rescue Medication**

All subjects are expected to assess their postoperative pain intensity and pain relief according to the pain intensity and pain relief schedule following the administration of study medication; those PI and PR assessments are referenced as the scheduled PIs and PRs. Subjects who require rescue analgesia are expected to report their pain intensity and pain relief within 5 minutes before taking the rescue medication; these PI and PR are referenced as the pre-rescue PI and PR. When the assessment of a scheduled PI and PR are done after the rescue medication the scheduled PI and PR scores will be replaced by the pre-rescue PI and PR scores for the purpose of efficacy analysis. This method is referenced as the Last Observation Carried Forward (LOCF). The original scheduled PI and PR scores will be displayed on data listing along with the ‘imputed’ PI and PR scores.

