The following efficacy assessments will be completed by the subjects at 15, 30, and 45 min and at 1, 1.5, 2, 3, 4, 5, 6, 7, and 8 hours after study medication administration, as well as within 5 minutes prior to first use of rescue medication and at early termination from the study, if it occurs. Subjects will be asked to record responses for the following assessments, in order:

- Pain intensity (PI) using the 11-point Numerical Pain Rating Scale (NPRS).
- Pain relief (PR) using a 5-point categorical scale (where 0= no pain relief, 1= little pain relief, 2= some pain relief, 3= a lot of pain relief, 4= complete pain relief).

In addition, at 8 hours post-dose or within 5 minutes prior to first use of rescue medication (whichever is earlier), subjects will be asked to record within the provided patient diary:

• 'Patient Rating of Treatment Satisfactoriness' using a 5-point verbal rating scale (0=poor,1=fair, 2 =good, 3=very good, 4=excellent).

Randomized subjects will remain NPO (nil per oral or nothing by mouth), including water, from Check-in (i.e., at least 2 hours before the administration of the dose of study medication to randomized subjects) until 2 hours post-dose, on Day 1 (study day). After 2 hours post-dose, subjects may be permitted to consume water, or gelatin snacks. Subjects are prohibited from ingesting solid foods or carbonated beverages for at least 6 hours post-dose.

Safety assessments will include 12-lead ECGs, vital sign parameters, physical exam and clinical labs. 12-lead ECGs will be performed before surgery, at baseline (before administration of the study treatment) and repeated at 1, 2, 4 and 8 hours post-dose, with a window period of \pm 45 minutes for each timepoint. Vital sign parameters (sitting pulse rate, sitting or supine blood pressure and respiratory rate) will be measured and recorded before surgery, at baseline, 1, 2,

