8.0 Efficacy Evaluation

8.1 Overview of Analysis Issues

8.1.1 Handling of Dropouts or Missing/Invalid Data

Subjects with missing or invalid PI NPRS data will be imputed using the following rules.

Subjects who require rescue medication will record their pain intensity (PI) NPRS, Pain Relief (PR) and Patient Rating of Treatment Satisfactoriness scores within 5 minutes prior to first use of rescue medication. These are referred to as 'pre-rescue' PI, PR, and Patient Rating of Treatment Satisfactoriness scores, respectively. Any scheduled PI or PR assessments scheduled within 4 hours after administration of rescue medication will be replaced by the pre-rescue score in the efficacy analysis. This method of replacement is referred to as the windowed Last Observation Carried Forward (wLOCF).

After any scheduled PI/PR scores within 4 hours after rescue are appropriately replaced by the pre-rescue PI/PR scores, any other scheduled PI/PR scores that are still missing intermittently and are not within 4 hours after rescue medication will be imputed using linear interpolation between adjacent observed values.

After all intermittent missing scores are imputed, any scheduled PI/PR scores missing because the subject dropped out of the study will be imputed as follows: If the subject drops out due to adverse event (AE), the PI score will be imputed using a baseline observation carried forward (BOCF) method; if the subject drops out for other reasons, the PI/PR score will be imputed using the last observation carried forward (LOCF) method. PI data with missing baseline PI score will be excluded from the analysis.

For responder endpoints, subjects that drop out will be considered as non-responders for all assessment time points after their date/time of drop out. Similarly, if a subject receives rescue medication, then the subject will be treated as a non-responder for all subsequent timepoints.

No imputation for other efficacy or safety will be performed.

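### SAP 8.1.1: baseline carry-forward after an AE exit can hide worsening pain, and the last observation carried forward for other early leavers is undefined

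*Protocol*

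**What the plan says.** **Collection.** Protocol 6.5.4 has the pain assessments "scheduled at the 8-hour post dose time point should be collected at the time of early study termination (if it should occur". It sets no condition about recent rescue. SAP 2.2 lists this score beside the fixed times: subjects rate pain at those times "as well as within 5 minutes prior to first use of rescue medication and at early termination from the study, if it occurs". The early-termination score is therefore additional to the scheduled ones.

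**Imputation.** SAP 8.1.1 works in order:

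1. Rescue: "Any scheduled PI or PR assessments scheduled within 4 hours after administration of rescue medication will be replaced by the pre-rescue score".
2. Scores still missing intermittently, outside that 4-hour window, are interpolated linearly.
3. Dropout: "After all intermittent missing scores are imputed, any scheduled PI/PR scores missing because the subject dropped out of the study will be imputed as follows". There are two branches:
   - AE exits: "If the subject drops out due to adverse event (AE), the PI score will be imputed using a baseline observation carried forward (BOCF) method". This branch is worded for pain intensity (PI) only and has no exception.
   - Other exits: "if the subject drops out for other reasons, the PI/PR score will be imputed using the last observation carried forward (LOCF) method". The last observation is not defined.

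**Protocol rule on rescue.** Protocol 8.3.2.1 substitutes the pre-rescue scores with no 4-hour limit: "When the assessment of a scheduled PI and PR are done after the rescue medication the scheduled PI and PR scores will be replaced". Protocol 3.1 says of assessments after rescue: "However, these assessments will be disregarded in the statistical analysis". Protocol 8.3.1 lets the SAP prevail where the two differ.

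**The concern.** **AE exits.** Setting PI to baseline is meant to give no credit for relief once a subject leaves because of an AE. It does that when pain had improved. When the last score was above baseline, the same rule removes an observed worsening: the pain intensity difference (PID) becomes 0 and SPID improves.

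**Other exits.** The replacement rule covers scheduled scores. An early-termination score taken between scheduled times is not one of them. Read literally, such a score taken within 4 hours after oxycodone/acetaminophen escapes replacement, is the last value observed, and could be carried to the time points beyond the window. A score affected by rescue would then stand as the result of study treatment.

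At stake are SPID6 (primary) and SPID8 for both branches, and TOTPAR for the second.

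**Working it through.** The plan gives no figure on this point, so there is none to reproduce. All individual scores below are assumed. They show how the rules act, not what the trial will contain.

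**Inputs from the documents**
- Scheduled times: 0.25, 0.5, 0.75, 1, 1.5, 2, 3, 4, 5, 6, 7, 8 h (SAP 8.2.1).
- SPID: trapezoidal rule on PID, points chosen by nominal time (SAP 8.2.2).
- Baseline NPRS at least 5, so pain can rise by up to 5 points (SAP 2.2).
- Arm size: 120 / 4 = 30 (SAP 2.5, 2.6).
- Delay of rescue to 2 h is encouraged, not required (SAP 2.2).

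I use nominal times and NPRS-hours, with improvement positive. The SAP works in minutes and shows improvement as negative.

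**Formula.** Two imputations differ by *g* points from scheduled time *n* onward and agree at the preceding scheduled time *p*. Their difference in SPID to hour *H* is *g* × [(*n* − *p*)/2 + (*H* − *n*)].

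**AE exit with pain above baseline.** Baseline 6, last score 9 at 2 h. Here *g* = 3, *p* = 2, *n* = 3. Baseline carried, compared with 9 carried:
- SPID6: 3 × (0.5 + 3) = 10.5 better; 10.5 / 30 = 0.35 on the arm mean.
- SPID8: 3 × (0.5 + 5) = 16.5 better; 16.5 / 30 = 0.55 on the arm mean.

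**AE exit with pain below baseline.** Baseline 7, last score 4 at 2 h. SPID6 is 3 × 3.5 = 10.5 worse under the baseline rule than if 4 were carried. The intended penalty works here.

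**Other exit within 4 h after rescue.** Baseline 7, pre-rescue 8, one rescue, early-termination score 3 taken between scheduled times one hour after rescue. Two readings of step 3:
- *Reading A:* the last value of the series left by steps 1 and 2 is carried. That is the pre-rescue 8, so there is no distortion.
- *Reading B:* scheduled points inside the window hold 8 from step 1, and the early-termination 3 fills the points beyond it. Here *g* = 8 − 3 = 5.

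| Rescue at | Window ends | First scheduled point beyond | SPID6, B over A | SPID8, B over A |
|---|---|---|---|---|
| 0.5 h | 4.5 h | 5 h | 5 × (0.5 + 1) = 7.5 | 5 × (0.5 + 3) = 17.5 |
| 1.5 h | 5.5 h | 6 h | 5 × 0.5 = 2.5 | 5 × (0.5 + 2) = 12.5 |
| 2 h | 6 h | 7 h | 0 | 5 × (0.5 + 1) = 7.5 |
| 3 h | 7 h | 8 h | 0 | 5 × 0.5 = 2.5 |
| 4 h | 8 h | none | 0 | 0 |

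A point exactly 4 h after rescue is counted as inside the window. Under reading B, SPID6 changes only if rescue came before 2 h; later rescue can touch only SPID8. For rescue at 1.5 h the arm-mean shift per subject is 2.5 / 30 = 0.08 (SPID6) and 12.5 / 30 = 0.42 (SPID8).

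**The case against.** The strongest reply is that SAP 8.1.1 never says the early-termination score is carried. Its steps are ordered, and carrying the last value of the already replaced series gives the pre-rescue score. Protocol 3.1 disregards assessments after rescue without limiting this to scheduled ones, and where the SAP is silent the two can be read together. An exit score that falls at a scheduled time within 4 hours after rescue is replaced anyway. All of this stands. It leaves an ambiguity, not an instruction to use a score taken under rescue, and a reader who infers such an instruction goes beyond the text.

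A reader might also infer that the exit score fills every missing point, including those inside the window. With rescue at 1.5 h that would add 5 × (0.5 + 3) = 17.5 to SPID6. Step 1 has already given the points inside the window the pre-rescue score, so the ordered text does not support this.

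On the AE branch, the reply is that baseline carry-forward is a standard penalty and usually costs the subject. That is right for subjects whose pain had improved. It does not answer the case of pain above baseline, where the rule as written has no exception. The case is narrow, though: rescue is available on request, and scheduled points within 4 hours after rescue already hold the pre-rescue score.

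The plan also contains checks. The per-protocol set (SAP 4.3) requires all pain assessments through 8 h, so early leavers drop out of the supplemental SPID and TOTPAR analyses (SAP 8.3). Responder analyses count dropouts as non-responders after they leave (SAP 8.1.1). These limit the harm, but the primary mITT analysis keeps both problems.

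**Conclusion.** The point holds in two parts of different strength. The AE rule, as written, scores a subject better than observed whenever the last valid NPRS was above baseline: by 10.5 NPRS-hours on SPID6 and 16.5 on SPID8 in the illustration. The rule for other exits leaves the carried value undefined; the effect is nil on one fair reading and, on the other, reaches SPID6 only for rescue before 2 h.

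The size is small. The 0.35 shift in arm-mean SPID6 is about 1% of 5 × 6 = 30 NPRS-hours, roughly full relief over 6 h from the lowest eligible baseline. The documents give no dropout rate, no count of such exits and no SD, so an effect on the test cannot be stated. Exits of this kind within 8 hours of confinement are probably few, which is an assumption.

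A reader might infer that the rules tilt the comparison, for example that more rescue on placebo shrinks the dose–placebo difference. The documents give no rescue or dropout rates by arm, so no direction is established. Priority: low, a clarification worth making before unblinding.

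**What to change.** Add two sentences to SAP 8.1.1 before unblinding:

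1. For dropout due to an AE, PI is imputed as the worse (higher) of baseline and the last valid score. This keeps the penalty for subjects who had improved.
2. The value carried forward, and the last valid score in sentence 1, is the last score not taken within 4 hours after rescue, whether scheduled or taken at early termination. A subject who leaves inside that window keeps the pre-rescue score to 8 h.

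The cost is the two sentences and a few lines of code. The few affected subjects receive slightly less favourable scores. Data collection and clinical procedures do not change.

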#### 6.5.5. End of Study Visit (Day 7 ± 3 days)

The following end of study safety assessments will be conducted for all subjects during the end of study visit on Day 7.

- Physical examination (Section 6.3.3)
- 12-lead ECG (Section 6.4.3)
- Resting Vital signs (Section 6.4.2)

- Clinical laboratory tests, only if there is a clinically significant abnormality or ongoing AE(s) (Section 6.4.1)
- Urine pregnancy test for women of childbearing potential (Section 6.4.1)
- Monitoring of AEs and concomitant medications (Section 7)

Change in concomitant medications after discharge will be documented and reviewed. Clinically significant adverse events, examination or test results will be followed until appropriate resolution can be documented.

In the event of early termination (ET), every attempt should be made to have the subject return to the site to complete procedures listed within this section and in [APPENDIX A](#):

The efficacy measures utilized in this study are commonly used in clinical studies performed in acute postoperative pain populations. The timing of assessments is intended to evaluate the time to onset of analgesia, duration of effect and magnitude of benefit.

The selected pharmacokinetic sampling times and parameters are appropriate to support the objectives of this study. Sample times will allow evaluation of the rate and extent of absorption of the study dose, and help in establishing exposure-response analysis, if any.

Safety measures used in this study are standard for clinical trials of investigational medications.

## **6.6. Clinical Stopping Rules**

This study will be discontinued if it is determined that there is a significant safety risk posed towards study subjects. Potential safety risks will be evaluated continuously throughout the course of enrollment in the study.

## 7. ADVERSE EVENTS

The investigator is responsible for the detection and documentation of events meeting the criteria and definition of an Adverse Event (AE), Serious AE (SAE), or Serious Suspected Adverse Reaction (SSAR) as provided in this protocol. During the study, when there is a safety evaluation, the investigator or site staff will be responsible for detecting AEs and SAEs, as detailed in this section of the protocol.

### 7.1. Definition of an Adverse Event

An AE is defined as any untoward medical occurrence associated with the use of a drug in humans, whether or not considered drug related.

An AE may be any unfavorable and unintended sign (including an abnormal laboratory finding), symptom, or disease temporally associated with the use of a study medication, whether or not considered causally associated with the use of the study medication. Any abnormal laboratory value deemed clinically significant by the investigator, regardless of causal relationship, must be reported as an AE.

Examples of an AE include the following:

- significant or unexpected worsening or exacerbation of the condition or indication under study
- exacerbation of a chronic or intermittent preexisting condition, including either an increase in frequency or intensity of the condition (e.g., abnormal physical examination finding)
- signs, symptoms, or clinical sequelae of a suspected interaction
- signs, symptoms, or clinical sequelae of a suspected overdose of the study medication or a concurrent medication (overdose per se should not be reported as an AE or SAE, unless non-serious or serious sequelae occur)
- symptoms or behavior suggesting cognitive or psychiatric disturbance

The following examples are not considered AE's:

- medical or surgical procedure (e.g., endoscopy, appendectomy), although the condition that leads to the procedure is an AE
- anticipated day-to-day fluctuations of preexisting disease(s) or condition(s) (including laboratory values) present or detected at the start of the study that do not worsen
- the disease or disorder being studied, or expected progression, signs, or symptoms of the disease or disorder being studied, unless they become more severe or occur with a greater frequency than expected for the subject's condition

All AE's, whether volunteered, elicited, or noted on physical examination, and regardless of causality or seriousness, will be assessed and recorded in the CRF beginning after administration of study medication through the final follow-up assessment (approximately  $7 \pm 3$  days after the last study drug administration). AE's will be assessed and recorded after administration of study medication through the Day 7

visit (see Sections 7.2 and 7.3). In addition, if the investigator becomes aware of the occurrence of a SAE within 30 days of the last visit, the SAE should be reported as outlined in Section 7.7.

